Appendix**Table 1.**

Pain score	Degree of pain	Response
0	None	Negative response to questioning.
1	Mild	Pain reported in response to questioning only, without any behavioral signs (withdrawal of extremity, grimacing, etc.)
2	Moderate	Pain reported in response to questioning and accompanied by a behavioral sign OR pain reported spontaneously without questioning
3	Severe	Strong vocal response OR spontaneous response accompanied by a behavioral sign

Table 2.

	Esmolol	Lidocaine	Placebo
Patients reporting pain	2	3	5
Total patients	5	5	5
Incidence of pain	40%	60%	100%

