Study Procedures, Interactions and Interventions

- Obtain informed consent and randomize patient into one of three groups (lidocaine, esmolol, placebo)
- Dose medications based on actual body weight
- Start 20 gauge IV in either extremity and hang lactated ringers (LR)
- Administer no sedative or analgesic (i.e., no Versed or fentanyl) prior to induction
- Place standard monitors and preoxygenate patient

- Administer study medication as a bolus
 - 1 mg/kg lidocaine to a max of 100 mg, 0.5 mg/kg esmolol to a max of 50 mg, or placebo
 - Lidocaine will be 20 mg/ml and esmolol will be 10 mg/ml
 - These concentrations allow us to simply administer 0.05 ml solution per kg regardless of which group the patient has been randomized into – 100 kg patient would receive 5 ml solution that would contain 100 mg lidocaine (= 1 mg/kg), 50 mg esmolol (= 0.5 mg/kg), or saline
 - Allow patient's IV to run freely
- 20-30 seconds after administration of study medication, bolus 0.5 mg/kg propofol to a max of 50 mg
- Record patient's pain over the next thirty seconds
 - Use the pain scale previously published by McCririck and Hunter (Anaesthesia 1990;45(6):443-4).
 - 0 = no pain
 - 1 = mild pain
 - Pain reported in response to questioning AND NOT accompanied by a physical sign (grimacing, withdrawal, tears, etc.)
 - 2 = moderate pain
 - Pain reported in response to questioning AND accompanied by a physical sign
 - Pain reported spontaneously AND NOT accompanied by a physical sign
 - 3 = severe pain
 - Pain eliciting a strong vocal response
 - Pain reported spontaneously AND accompanied by a physical sign
- Proceed with induction at the discretion of the attending anesthesiologist
 - If patient requires a NDMB, use vecuronium instead of rocuronium (due to venous irritation caused by rocuronium)
- Record vital signs every minute after induction for ten minutes
 - Also record administration of any medications given to treat hemodynamic derangements during this time frame (phenylephrine, ephedrine, propofol, etc.)
 - Do not administer esmolol for tachycardia during this time frame unless the patient shows evidence of myocardial ischemia or other significant derangements

Sample Size

150 patients (50 in each arm) is anticipated to be needed in this study.

Outcome Measure

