Our primary outcome measure will be the proportion of patients with pain using a pain scoring system previously used by studies looking at various remedies to decrease propofol injection pain (15, 17). In this scoring system, patients are observed and their responses and behaviors are rated according a specific rubric (Table 1) (17). This assessment will be performed by a blinded

member of the study team following administration of a sub-induction dose of propofol, 0.5 mg/kg up to 50 mg, just prior to full induction.

Our secondary outcome measure will be heart rate, blood pressure, and SpO₂ every minute following induction. We will record vital signs each minute for the first 10 minutes following induction.

Analytical Plan

In preparation for this study, we obtained pilot data using five patients in each of the three proposed study arms. As shown in Table 2, lidocaine and esmolol both decreased the incidence of propofol injection pain in relation to placebo. Given that 40% (95% CI 0-83%) and 60% (95% CI 17-100%) patients given lidocaine and esmolol respectively reported little to no pain defined as a pain score of 0 on our propofol pain injection while 0% of patients who received placebo reported no pain, we used a sample size calculator for proportions with a 25% difference considered clinically significant, 90% power, and a 95% confidence level to determine a sample size of 32. In order improve our certainty we will increase this to 50 patients per group.

We will perform descriptive statistics on all demographic data. We will perform an individual comparison of all three groups using Pearson's chi-square test with Bonferroni correction for multiple comparisons. Other inferential statistics will be performed as necessary.

Human Subjects Protection

Subject Recruitment Methods

Subjects will be identified through the daily review of the preanesthesia assessment clinic as well as the daily surgical schedule for those meeting inclusion criteria. They will then be approached by a member of the research staff regarding their participation.

Informed Consent

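### Do the two printed versions of the pain rubric leave the primary outcome undefined?

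*Combined protocol and SAP*

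**What the plan says.** The Outcome Measure section states: "Our primary outcome measure will be the proportion of patients with pain". It sends the reader to Table 1 for the rubric and has a blinded team member do the scoring. The Analytical Plan supplies the cut-point when it describes pilot patients who "reported little to no pain defined as a pain score of 0".

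The rubric itself appears twice, each time credited to the same published scale.

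- **Score 0.** The Study Procedures list says only that there is no pain. Table 1 says "Negative response to questioning".
- **Score 2, unprompted report.** The procedures list has "Pain reported spontaneously AND NOT accompanied by a physical sign". Table 1 has "pain reported spontaneously without questioning", with no condition on signs.
- **Score 3.** The procedures list has "Pain reported spontaneously AND accompanied by a physical sign", or pain that provokes a strong vocal reaction. Table 1 has "Strong vocal response OR spontaneous response accompanied by a behavioral sign".

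Neither version gives an order of precedence or a rule for a patient who does not answer.

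**The concern.** A primary outcome should give one answer per patient whichever page the assessor has open. Here an unprompted report with a grimace is 3 in the procedures list but fits both 2 and 3 in Table 1. A patient who cries out and then denies pain fits both 0 and 3 in Table 1. A patient who grimaces and denies pain is 0 in Table 1 and is not listed in the procedures. The wording "little to no pain defined as a pain score of 0" adds to the doubt, because the scale calls score 1 mild pain, and a reader might wonder on which side score 1 falls.

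Blinding keeps such inconsistency from favouring an arm, but it does not make scores repeatable. If patients in pain drifted into score 0, the placebo rate would rise from the assumed 0%, and the contrast with each active arm would shrink. A rule chosen after seeing the data would also be open to criticism.

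**Working it through.** **1. Is the cut-point settled?** Table 2 gives patients reporting pain as esmolol 2/5 = 40%, lidocaine 3/5 = 60%, placebo 5/5 = 100%. The Analytical Plan gives score 0 as 60%, 40% and 0%. Each pair sums to 100%, so everyone not at score 0 was counted as having pain, and score 1 is on the pain side. The planned sample size uses the same contrast. With 0% versus 25%, two-sided alpha 0.05 (sidedness is assumed) and 90% power, the unpooled formula gives

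n = (1.960 + 1.282)² × [0 × 1 + 0.25 × 0.75] / 0.25² = 31.52, rounded up to 32 per group, which is the stated figure.

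**2. Which patients are affected?** Cross four kinds of report with sign (yes/no) and strong vocal reaction (yes/no): 16 combinations. Two readings are needed. In the procedures list a strong vocal reaction is taken as pain-related. In Table 1 the spontaneous response is taken as a spontaneous report of pain.

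| Patient | Combinations | Procedures list | Table 1 | Pain yes/no |
|---|---|---|---|---|
| Reports pain unprompted | 4 | 2 or 3 | 2 or 3 | pain in both |
| Says yes when asked | 4 | 1, 2 or 3 | 1, 2 or 3 | pain in both |
| Says no; no sign, no strong vocal reaction | 1 | 0 | 0 | no pain in both |
| Says no; sign only | 1 | not listed | 0 | settled by Table 1 |
| Says no; strong vocal reaction, with or without sign | 2 | 3 | 0 and 3 | conflict inside Table 1 |
| No answer; strong vocal reaction, with or without sign | 2 | 3 | 3 | pain in both |
| No answer; no strong vocal reaction, with or without sign | 2 | none | none | open |

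Table 1 gives more than one score in 7 of 16 combinations and the procedures list in 3 of 16, but most of these overlaps lie within scores 1 to 3. For pain yes/no, 4 + 4 + 1 + 2 = 11 combinations agree. The other five are one settled by Table 1, two in conflict inside Table 1 and two open. In none does one version give only pain and the other only no pain. Any patient who reports pain, prompted or not, counts as pain in both. If the spontaneous response is instead read as any reaction, a sign followed by denial also becomes both 0 and 3 in Table 1.

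**3. How large could the effect be?** Pearson chi-square without continuity correction, 50 per arm, alpha 0.05/3 = 0.0167. With 0, 1, 2, 3 or 4 placebo patients at score 0, an active arm needs 6, 8, 10, 12 or 13 pain-free patients (p = 0.0115, 0.0144, 0.0138, 0.0117, 0.0166).

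Suppose a share m of patients in pain is scored 0. The pain-free rates become m on placebo and a + (1 − a)m on active, where a is the true active rate. Exact power by binomial enumeration:

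| a | m = 0 | m = 5% | m = 10% |
|---|---|---|---|
| 25% (planning minimum) | 99.3% | 84.1% | 67.5% |
| 40% (lidocaine pilot) | above 99.9% | 99.5% | 96.8% |
| 60% (esmolol pilot) | above 99.9% | at least 99.9% | at least 99.9% |

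In the other direction, suppose 10% or 20% of score-0 patients are counted as pain. The active rate becomes 0.25 × 0.9 = 22.5% or 0.25 × 0.8 = 20%, placebo stays at 0%, and power is the chance of at least 6 pain-free of 50: 98.1% or 95.2%. Every m here is an assumption.

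**The case for a change.** The strongest case for acting is that the outcome text points to Table 1 while the procedures tell staff to score from their own list, so both are live during the trial. The crossing cases are plausible in a thirty-second window after a propofol bolus. The pilot cannot exclude them: with 0 of 5 placebo patients at score 0, the one-sided 95% upper limit for that rate is 1 − 0.05^(1/5) = 45%. Aligning the text would cost almost nothing.

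Some of this stands. The versions differ at score 2 and in the wording of scores 0 and 3, Table 1 has no precedence line, and a silent patient without a strong vocal reaction has no score.

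The rest is weaker. In Table 1 the severe row follows a row about pain reported spontaneously, so its spontaneous response reads naturally as shorthand for the same thing, in line with the procedures list. The conflict between 0 and 3 then needs a strong vocal reaction followed by denial. The 84.1% and 67.5% figures move patients one way only, at a rate taken from nowhere in the documents. Nor would tidier text recover that loss where the cause is a sign with denial: if self-report remains the definition, those patients score 0 before and after. The significance bar does rise by about two patients per placebo patient at score 0, but by only one from three to four, and that count holds the active arm fixed although the same rule would apply there. Extra check-boxes and a sensitivity analysis are a matter of preference.

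**Conclusion.** The inconsistency is real but does not undermine the primary result. The largest mismatch, between scores 2 and 3, cannot alter a pain/no-pain outcome, and the plan names no severity analysis. The 0 versus 1–3 cut follows from the Analytical Plan and Table 2 together; the loose phrase about little pain is a slip. A sign with pain denied is 0 under the rubric that the outcome section names.

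Two residual cases remain: a strong vocal reaction followed by denial, and no answer without a strong vocal reaction. The first is settled by the procedures list, or by the ordinary habit of taking the highest score that applies. The second is a missing-outcome question that a statistician would settle before unblinding and report by arm. The plan allows no sedative or analgesic before induction and gives no sign that silent patients are expected.

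The effect on the result cannot be quantified from the documents. It would matter only if the true difference were near 25 points and the affected patients were fairly common. This conclusion rests on the binary outcome with score 0 as no pain, on reading Table 1's spontaneous response as a report of pain, and on blinded scoring. Aligning the two printings would be good housekeeping, but it does not change the endpoint, the test or the sample size.
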